### **11.1. Treatment of Missing and Spurious Data**

See general definitions in chapter 5.4

### **11.2. Exclusion of Particular Information**

No data are excluded from the analysis from the above analysis set and variables.

### **11.3. Descriptive Analyses**

See general definitions in chapter 5.1 and exceptions for reporting numbers and text below the variable tables, if appropriate.

In addition, boxplots will be generated.

### **11.4. Hypotheses & Statistical Tests**

There are no pre-defined statistical hypotheses.

## 12. Secondary Endpoint2

CIP chapter 7.2.2: Secondary endpoints

### Noise burden

The secondary endpoint 2 evaluates the noise burden at the 1st follow-up and at 3-month follow-up by retrieving the percentage of noise via the programmer.

### 12.1. Analysis set

All analyses are performed for the full analysis set.

### 12.2. Variables

| Data file, identifier patient_display_id_full | Notes | Variable name | Variable label | Variable level | Nominal values |
|---|-------|---------------|----------------|----------------|----------------|
| follow_up_1st                                 |       | DUNSE         | Noise [%]      | Scale          |                |
| follow_up_3months                             |       | DUNSE         | Noise [%]      | Scale          |                |
| follow_up_12months                            |       | DUNSE         | Noise [%]      | Scale          |                |

Moreover, the proportions of patients with "Noise smaller 5% vs. at least 5%" will be reported for the 1 month FU, 3 months FU and 12 months FU separately and in total (all FU together). Therefore the variable "DUNSE" will be recoded accordingly.

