Fifty adverse events (AEs) were reported until the end of the 3-month follow-up. Two SADEs were reported in two patients with risk of erosion and subsequent explantation of the BioMonitor 2. The SADE-free rate was statistically significant higher than 90%. The primary endpoint was met.

The mean R-wave amplitude at the 1-week follow-up visit was 0.75 mV and demonstrated significant superiority to the R-wave amplitude of the predecessor BioMonitor (0.3 mV). Thus, the secondary endpoint was met. Moreover, the BioMonitor 2 showed a low and stable noise burden, which had a mean value of 3.0% and 3.4% at the 1-week and 3-month follow-up, respectively.

All endpoints were met. The study results confirm the safety and efficacy of the BioMonitor 2 system and show that the insertion procedure performance was overall rated between 'good' and 'acceptable' by the investigators^{22,23}. A publication has been accepted⁶⁴.

⁵ Clinical Investigation Report of the BIO|Master.BioMonitor 2 Study of the Implantable Cardiac Monitor BioMonitor, Version 1.0. 2017

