7.2.2 Secondary endpoints

The following 4 secondary endpoints are defined for the study.

R-wave amplitude

The **secondary endpoint 1** evaluates the R-wave amplitude at the 1st follow-up and at 3-month follow-up by measuring both, the lowest and the highest amplitude value via the programmer.

Noise burden

The **secondary endpoint 2** evaluates the noise burden at the 1st follow-up and at 3-month follow-up by retrieving the percentage of noise via the programmer.

Assessment of P-wave visibility

The **secondary endpoint 3** evaluates the P-wave visibility at 1st, 3- and 12-month follow-up. The investigator will evaluate whether P-waves can be recognized in the stored sECGs showing sinus rhythm. The number of heart cycles and observed P-waves which can undoubtedly be identified in ECGs will be assessed by the investigator.

SADE-free rate until the 12-month follow-up

The **secondary endpoint 4** is the SADE-free rate related to the BIOMONITOR III 12 months after insertion.

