8.3.5.4 Drop-out according to protocol

The investigator shall exclude a patient due to the following reasons and after all adverse events have been reported and the corresponding eCRFs have been thoroughly completed:

- Patient with no insertion attempt of the BIOMONITOR III within 4 weeks of enrollment
- Patients in whom the insertion fails and no new attempt is planned are terminated after complete reporting of the insertion attempt and all adverse events connected to the failed insertion.
- Patients in whom the BIOMONITOR III was replaced/explanted/deactivated are terminated after complete reporting of the explantation and all adverse events connected to the explantation.

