## 5. General Statistical Procedures

### 5.1. Descriptive analyses

CIP chapter ...

...

For continuous variables descriptive statistics (mean, standard deviation, minimum, 1. quartile, median, 3. quartile and maximum) will be calculated. For nominal variables absolute numbers and relative frequencies based on the non-missing data will be determined. Ordinal data are described by the 1st quartile, median, and 3rd quartile as well as the absolute numbers and relative frequencies based on the non-missing data of each category.

For illustration, see the following standard tables with and without subgroup analyses based on dummy data.

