## 5.7. Interim analyses

### CIP chapter 11.6: Provisions for an interim analysis

The main differences between BioMonitor 2 and BIOMONITOR III are limited to a reduced device size and a novel simplified injection-like insertion procedure. The focus of this study is primarily on the safety of the BIOMONITOR III system including the insertion procedure.

Therefore the primary endpoint is to evaluate the SADE-free rate related to the BIOMONITOR III and the incision and insertion tool set from insertion until the 3-month follow-up. When all enrolled patients have either completed the 3-month follow-up or their study participation has been terminated, the data for the primary endpoint are completed. At this point in time, an interim Clinical Investigation Report will be written. The content of this report will be pre-defined in a Statistical Analysis Plan.

Individual data collected in this study, which do not concern the primary endpoint, may be analysed before the study is completed. If they shall be published, the stipulations of section 21 apply. Safety reasons, the support of regulatory submissions and publication opportunities may trigger unscheduled interim analyses.

Such unplanned interim analyses and reports, if any, will contain at least descriptive statistics of baseline and insertion data and descriptive statistics of the defined endpoints. Inferential statistics of endpoints may be included to support publication activities. The precise scope of each interim analysis will be defined in the SAP before the individual interim analyses.

In case of a suspension of the clinical investigation, an interim analysis will be performed to generate a clinical investigation report according to the MDR requirements. No multiplicity adjustment is foreseen.

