### 13.5. Descriptive Analyses

[figure not shown]
See general definitions in chapter 5.1 and exceptions for reporting numbers and text below the variable tables, if appropriate.

In addition, boxplots will be generated.

Moreover, the rate of patients with a P-wave visibility of at least 5% shall be reported for each follow-up separately and the number of patients with a P-wave visibility of at least 5% at all available follow-ups shall be reported.

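### Does the all-visit noise share in SAP 12.2 need a written rule for combining a patient's follow-ups?

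*SAP*

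**What the plan says.** CIP 7.2.2 states that secondary endpoint 2 "evaluates the noise burden at the 1st follow-up and at 3-month follow-up by retrieving the percentage of noise via the programmer". The excerpt at the head of SAP section 12 repeats this: the endpoint "evaluates the noise burden at the 1st follow-up and at 3-month follow-up". Neither names the 12-month visit.

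SAP 12.2 then lists the noise variable DUNSE at the 1st, 3-month and 12-month follow-up. It asks for the share of patients below 5% versus at least 5%, which "will be reported for the 1 month FU, 3 months FU and 12 months FU separately and in total (all FU together"). The one derivation step is that DUNSE is recoded. SAP 12.2 defines no patient-level variable and shows no footnote mark.

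The general rule for nominal data in SAP 5.1 is that "absolute numbers and relative frequencies based on the non-missing data will be determined". It is silent on repeated visits. For P-waves, SAP 13.5 does give a rule across visits: "the number of patients with a P-wave visibility of at least 5% at all available follow-ups shall be reported".

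On timing, SAP 5.7 has a report once the 3-month data are complete: "At this point in time, an interim Clinical Investigation Report will be written".

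**The concern.** A patient can have one, two or three noise readings, yet the total is described as a share of patients. It could mean patients below 5% at every visit, patients below 5% at one visit or more, patients whose mean is below 5%, or simply all readings counted together. These give different numbers from the same data. SAP 13.5 shows that the authors could write such a rule when they wanted one.

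The total also draws in a visit that the endpoint does not name. If it appeared in both the interim and the final report, it could rest on two visits in the first and three in the second. Under an every-visit or any-visit rule it would then move without any change in noise. At stake is whether readers could compare one summary figure between reports, or with other devices.

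**Working it through.** The plan states no figure for this total, so there is none to reproduce. The check has four steps.

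**1. What the text leads an analyst to do.** DUNSE is recoded on each form and keeps one name on all three. R-wave and P-wave variables are handled differently: SAP 11.2 renames its readings by visit, and SAP 13.2 defines separate derived variables for pooled and total visibility. Where a patient-level rule is wanted, SAP 13.5 writes it. Taking all follow-ups together after a recode therefore points to pooled readings. With visit shares p1, p2, p3 on n1, n2, n3 readings:

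- total = (n1·p1 + n2·p2 + n3·p3) / (n1 + n2 + n3)

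Every term is already in the per-visit lines. A reader who wants only the two endpoint visits can compute (n1·p1 + n2·p2) / (n1 + n2).

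**2. How far other rules would differ.** The only data on level are for the predecessor device (CIP 5.2.4), "which had a mean value of 3.0% and 3.4% at the 1-week and 3-month follow-up". No distribution is given. If noise were exponential, the share below 5% would be 1 − exp(−5/3.0) = 81% and 1 − exp(−5/3.4) = 77%. I assume p = 80% at each visit, complete data, and within-patient correlation ICC of 0.3, 0.5 or 0.7. In a beta-binomial model with s = (1 − ICC)/ICC and a = p·s:

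- P(all three below 5%) = (a/s) · (a+1)/(s+1) · (a+2)/(s+2)
- P(at least one below 5%) = 1 − the same product with 1 − p in place of p

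For ICC 0.5, s = 1 and a = 0.8. All three: 0.8 × 1.8/2 × 2.8/3 = 0.672. At least one: 1 − 0.2 × 1.2/2 × 2.2/3 = 0.912.

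| ICC | all three | pooled | at least one | spread, all to any |
|---|---|---|---|---|
| 0.3 | 61.4% | 80% | 95.0% | 34 points |
| 0.5 | 67.2% | 80% | 91.2% | 24 points |
| 0.7 | 72.5% | 80% | 86.9% | 14 points |

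At p = 90% the spreads are 19, 14 and 8 points. For scale, the 95% half-width at 80% with 141 patients is 1.96·√(0.8 × 0.2/141) = 6.6 points. So the rules do differ, but the whole spread lies between two rules that section 12 does not contain.

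**3. Interim versus final report.** Under the all-visits rule, going from two visits to three lowers the share from 68.8% to 61.4%, from 72.0% to 67.2%, or from 75.2% to 72.5% (ICC 0.3, 0.5, 0.7). Under pooling it stays at 80%. If the 12-month share really were lower, say 74%, the pooled total with equal numbers would be (80 + 80 + 74)/3 = 78%, and the 12-month line would show why.

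The two-then-three pattern is not certain either. On the approximate dates in CIP 8.3.7, a last consent on 31 May 2020, plus 28 days to insertion (CIP 9.3), plus 91 + 14 days, reaches 11 October 2020. A first insertion on 1 September 2019 makes the 12-month visit possible from 18 August 2020 (12 months less 14 days). The periods can overlap. The SAP also does not say that this total appears in the interim report.

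**4. The 12-month visit.** CIP 9.5.2 and Table 3 have noise measured at every follow-up, so the reading is planned data. SAP 11.2 likewise tabulates R-wave values at insertion and 12 months, although that endpoint names only the 1st and 3-month visits. Showing more visits than an endpoint names is this SAP's regular practice. The phrase for a 1-month visit in SAP 12.2 is a slip for the 1st follow-up, which falls at 10 days to 4 weeks.

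**The case for a change.** The best argument for a change is that SAP 1.1 sets out to give full instructions for descriptive output, and here two programmers could follow the text and report different totals. The text says patients, and pooled readings are not patients: with complete data in 141 patients the denominator would be 3 × 141 = 423. One sentence would settle it.

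Much of that stands. The unit and denominator are not stated, and pooling fits the word patients badly. There is also a trap if a confidence interval is put on the pooled total. Treating 423 readings as independent gives a half-width of 1.96·√(0.8 × 0.2/423) = 3.8 points. Allowing for clustering with factor √(1 + 2·ICC) gives 4.8, 5.4 and 5.9 points at ICC 0.3, 0.5 and 0.7. SAP 5.2 promises intervals for the secondary endpoints' parameters but does not name this total, and a statistician would account for repeated readings or leave the interval off.

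What does not follow is that a new rule would improve the plan. The obvious candidate, patients below 5% at both endpoint visits among those with both readings, is a different output from the one requested. It drops patients who leave between visits. CIP 8.3.5.4 makes that a real group: "Patients in whom the BIOMONITOR III was replaced/explanted/deactivated are terminated after complete reporting of the explantation". They may include patients with poor sensing. That rule would exchange a labelling question for a selection question.

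**Conclusion.** No change is needed. The SAP leaves one descriptive line under-specified, and the 12-month visit in it goes beyond secondary endpoint 2 as defined. Both observations are correct. Neither leads to a wrong conclusion. The natural reading is a pooled share that can be rebuilt from the visit lines, and the two endpoint visits are reported on their own. SAP 5.3 treats everything outside the primary endpoint as exploratory, SAP 12.4 sets no hypothesis for noise, and CIP 11.5 ties pass or fail to the primary test alone.

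The possible difference between rules, 14 to 34 points at an assumed 80% per visit, rests on an assumed share, an assumed correlation and complete data. It arises only if an analyst adopts a rule that the noise section does not state. Whoever builds the table has to write a row title and a denominator, and that step settles the unit without an amendment. The judgement would differ if a claim or a test rested on the total. None is visible in the documents, although the list of promotional claims in CIP 7.3 is redacted and cannot be checked.

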### 12.1. Treatment of Missing and Spurious Data

See general definitions in chapter 5.4

### 12.2. Exclusion of Particular Information

No data are excluded from the analysis from the above analysis set and variables.

### 12.3. Descriptive Analyses

See general definitions in chapter 5.1 and exceptions for reporting numbers and text below the variable tables, if appropriate.

In addition, boxplots will be generated.

### 12.4. Hypotheses & Statistical Tests

There are no pre-defined statistical hypotheses.

## 13. Secondary Endpoint3

[figure not shown]
CIP chapter 7.2.2: Secondary endpoints

### Assessment of P-wave visibility

*The secondary endpoint 3 evaluates the P-wave visibility at 1st, 3- and 12-month follow-up. The investigator will evaluate whether P-waves can be recognized in the stored sECGs showing sinus rhythm. The number of heart cycles and observed P-waves which can undoubtedly be identified in ECGs will be assessed by the investigator.*

### 13.1. Analysis set

All analyses are performed for the full analysis set.

[figure not shown]
### 13.2. Variables

| Data file, identifier patient_display_id_full | Notes | Variable name                    | Variable label                               | Variable level | Nominal values |
|---|-------|----------------------------------|--|----------------|----------------|
| follow_up_1st                                 |       | EGCCCNUM01                       | Exact number of cardiac cycles               | Scale          |                |
| follow_up_1st                                 |       | EGPWNUM01                        | Exact number of clearly identifiable P-waves | Scale          |                |
| sar_data                                      |       | sar_pwavevis_fu1_1  | P-wave visibility FU1 1st [%]                |                |                |
| follow_up_1st                                 |       | EGCCCNUM02                       | Exact number of cardiac cycles               | Scale          |                |
| follow_up_1st                                 |       | EGPWNUM02                        | Exact number of clearly identifiable P-waves | Scale          |                |
| sar_data                                      |       | sar_pwavevis_fu1_2  | P-wave visibility FU1 2nd [%]                |                |                |
| sar_data                                      |       | sar_pwavevis_fu1_t  | P-wave visibility pooled [%]                 |                |                |

|                    |  |                                 |  |       |  |
|--------------------|--|---------------------------------|--|-------|--|
| follow_up_3months  |  | EGCCCNUM -> EGCCCNUM_3m         | Exact number of cardiac cycles               | Scale |  |
| follow_up_3months  |  | EGPWNUM -> EGPWNUM_3m           | Exact number of clearly identifiable P-waves | Scale |  |
| sar_data           |  | sar_pwavevis_fu3   | P-wave visibility 3m [%]                     |       |  |
|                    |  |                                 |  |       |  |
| follow_up_12months |  | EGCCCNUM -> EGCCCNUM_12m        | Exact number of cardiac cycles               | Scale |  |
| follow_up_12months |  | EGPWNUM -> EGPWNUM_12m          | Exact number of clearly identifiable P-waves | Scale |  |
| sar_data           |  | sar_pwavevis_fu12  | P-wave visibility 12m [%]                    |       |  |
| sar_data           |  | sar_pwavevis_tot   | P-wave visibility total [%]                  |       |  |
|                    |  |                                 |  |       |  |

### 13.3. Treatment of Missing and Spurious Data

See general definitions in chapter 5.4

### 13.4. Exclusion of Particular Information

No data are excluded from the analysis of the above analysis set and variables.

Also data from the 3 months and 12 months FU which are outside the defined time range will be considered her.

### 13.5. Descriptive Analyses

[figure not shown]
See general definitions in chapter 5.1 and exceptions for reporting numbers and text below the variable tables, if appropriate.

In addition, boxplots will be generated.

Moreover, the rate of patients with a P-wave visibility of at least 5% shall be reported for each follow-up separately and the number of patients with a P-wave visibility of at least 5% at all available follow-ups shall be reported.

### 13.6. Hypotheses & Statistical Tests

There are no pre-defined statistical hypotheses.

## 14. Secondary Endpoint4

CIP chapter 7.2.2: Secondary endpoints

SADE-free rate until the 12-month follow-up

The secondary endpoint 4 is the SADE-free rate related to the BIOMONITOR III 12 months after insertion.

### 14.1. Analysis set

All analyses are performed for the full analysis set.

For the calculation of the Kaplan-Meier analysis, the following time variables will be used:

1. For patients with at least one primary endpoint: time from insertion to time of first primary endpoint (sar\_aestdt\_first).
2. For patients without primary endpoint: time from insertion to last information available (sar\_time\_max).

For the KM analysis data of all patients is used.

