## 8. Data for a CONSORT diagram and “study realization”

The following data shall be reported:

- Number of patients with enrollment data
- Number of enrollments per site
- Date of FPI, LPI, LPO per site and total
- Cumulative and mean/median FU duration from insertion to last available CRF information
- Cumulative and mean/median FU duration from enrollment to termination date on termination CRF

The following variables will be calculated:

| Data file, identifier patient_display_id_full | Variable name | Variable label    | Variable Level | Nominal values |
|---|---------------|-------------------|----------------|----------------|
| insertion                                     | PRIMSTDT      | Date of insertion | date           | n.a.           |

|                     |                                 |   |       |      |
|---------------------|---------------------------------|---|-------|------|
| enrollment          | dmicdt                          | Date of informed consent                              | date  | n.a. |
| Follow-up_1st       | svstdt -> svstdt_fu1            | Date of visit 1. FU                                   | date  | n.a. |
| Follow-up_3months   | svstdt -> svstdt_fu3m           | Date of visit 3 months FU                             | date  | n.a. |
| Follow-up_12months  | svstdt -> svstdt_fu12m          | Date of visit 12 months FU                            | date  | n.a. |
| hospitalization_log | hostdt                          | Hospitalization Start date                            | date  | n.a. |
| data_sar            | sar_hospstdt_first  | onset date of first hosp.                             | date  | n.a. |
| data_sar            | sar_hospndt_last    | date of resolution/death of last AE                   | date  | n.a. |
| adverse_event       | aestdt                          | Onset Date of AE                                      | date  | n.a. |
| data_sar            | sar_aestdt_first    | onset date of first AE                                | date  | n.a. |
| data_sar            | sar_aeendt_last     | date of resolution/death of last AE                   | date  | n.a. |
| termination         | dstrdt                          | Date of study termination                             | date  | n.a. |
| data_SAR            | sar_last_crf        | Date of last CRF information                          | date  | n.a. |

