|                     |                                 |   |       |      |
| data_SAR            | sar_time_crf        | time [days] from insertion to last CRF                | scale |      |
| data_SAR            | sar_time_term       | time [days] from insertion to termination             | scale |      |
| data_SAR            | sar_time_max        | time [days] from insertion to termination or last CRF | scale |      |

For all patients with premature study duration or missing insertion or any violation of in-/exclusion criteria the following variables shall be listed:

- All in-/exclusion criteria
- Date of enrollment
- Date and reason of premature study termination
- Date and type of all other available CRFs (except for AE-CRFs)

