### 10.1. Analysis set

The number of patients with at least one primary endpoint until the 3 months FU (the numerator) will be determined by assessing the variable "AERELPET" in the "AE evaluation" form. This form is filled by the AE evaluation board and the variable "AERELPET" is set to "Yes" if and only if all conditions defined in 7.2.1 in the CIP are met.

The denominator will be calculated as follows:

1. The number of patients with 3 months FU will be counted by the number of non-missing entries in SVSTDT in the "3 month FU" form.
2. The number of patients with primary endpoint will be calculated as defined above.
3. In case of patients lying in the intersection of both sets, these patients will be counted once.
4. Patients without SADE and termination date less than 77 days after insertion will be disregarded.

Patients who do not attend the 3 months FU, but who have not terminated study participation earlier than 77 days after insertion will be included in the analysis.

For the calculation of the Kaplan-Meier analysis, the following time variables will be used:

1. For patients with at least one primary endpoint: time from insertion to time of first primary endpoint [REDACTED]
2. For patients without primary endpoint: time from insertion to last information available [REDACTED]

For the KM analysis data of all patients is used.

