### 14.2. Variables

| Data file, identifier patient_display_id_full | Notes   | Variable name | Variable label                                 | Variable level | Nominal values |
|---|---|---------------|--|----------------|----------------|
|   |   |               |  |                |                |
| AE evaluation                                 | sorted by patient_display_id_full and AESTDT and removed duplicates | AERELPET      | Adverse event is relevant for primary endpoint | nominal        | Yes
No      |

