## **14.5. Descriptive Analyses**

A Kaplan-Meier analysis (including Kaplan-Meier plot) will be calculated and the estimation of the SADE-free rate (including two-sided 95% confidence interval) at 12 months (= 365 days) will be given.

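### SAP 14.1 asks for time to the first primary endpoint but names a variable labelled as the first AE, so the 12-month Kaplan-Meier curve could place some SADEs too early

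*SAP*

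**What the plan says.** Secondary endpoint 4 is the "SADE-free rate related to the BIOMONITOR III 12 months after insertion". SAP 14.5 asks for a Kaplan-Meier plot and states that "the estimation of the SADE-free rate (including two-sided 95% confidence interval) at 12 months (= 365 days) will be given".

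SAP 14.1 defines the two times that feed the curve:

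- Event patients: "For patients with at least one primary endpoint: time from insertion to time of first primary endpoint", with sar_aestdt_first named as the variable.
- All other patients: time from insertion to the last available information, with sar_time_max named.

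SAP 8 defines both variables. It labels sar_aestdt_first "onset date of first AE", gives it level date, and places it directly under the onset date from the adverse_event file. It labels sar_time_max "time [days] from insertion to termination or last CRF". The section's stated purpose is study realization, for example "Cumulative and mean/median FU duration from insertion to last available CRF information".

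SAP 14.2 lists one variable for this endpoint, AERELPET, labelled "Adverse event is relevant for primary endpoint". According to SAP 10.1, the board sets it to Yes "if and only if all conditions defined in 7.2.1 in the CIP are met".

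**The concern.** The wording in 14.1 calls for the date of an adjudicated endpoint event. The label in SAP 8 describes the first AE of any kind. Nothing in 14.1 or 14.2 links sar_aestdt_first to AERELPET.

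A programmer who follows the label would count the right patients as having an event but could give them the wrong date. A patient with, say, insertion-site pain in week 1 and a SADE in week 10 would step the curve down in week 1. SAP 14.5 requires the plot as well as the day-365 figure, and CIP 5.3 argues that ICM complications mostly arise early. The timing shown on the plot therefore matters to the reader, even though no test depends on it.

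**Working it through.** **Side by side**

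| Place | Content |
|---|---|
| SAP 14.1, wording | First primary endpoint |
| SAP 8, label of the named variable | First AE, no endpoint restriction |
| SAP 1.2, example of a derived variable | Date of the first AE episode |
| SAP 8, row below | Resolution or death date of the last AE |

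A first-AE and last-AE pair fits the follow-up-duration purpose of SAP 8. It does not fit endpoint timing.

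**The plan's own figures.** The documents give no figure for secondary endpoint 4. The size used below, N = 157, reproduces: the normal approximation gives 132.78, so 133. Exact binomial power stays above 90% from n = 141, and 141/0.9 = 156.7, so 157.

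**How many SADE patients would be mistimed.** Inputs from CIP 5.2.4 (predecessor study): 50 AEs to 3 months, 2 of them SADEs, 92 enrolled. CIP 7.2.1 gives 91 days for 3 months and 105 days as the outer window.

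- Rate of other AEs: r = (50 − 2)/92/91 = 0.00573 per day.
- Chance that a SADE on day d has an earlier AE: 1 − exp(−r·d).
- SADE onset uniform over days 0–105: 1 − [1 − exp(−105r)]/(105r) = 1 − (1 − 0.548)/0.602 = 0.249.
- SADE onset exponential with mean 30 days, truncated at 105 (λ = 1/30): 1 − [λ/(λ+r)]·[1 − exp(−105(λ+r))]/[1 − exp(−105λ)] = 1 − 0.8532 × 0.9835/0.9698 = 0.135.

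| AE assumption | Uniform onset | Early-weighted onset |
|---|---|---|
| Predecessor rate | 0.249 | 0.135 |
| Same, clustered in patients (negative binomial, k = 0.5) | 0.195 | 0.113 |
| Half the rate | 0.136 | 0.072 |
| Double the rate | 0.419 | 0.240 |

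At the expected 3% SADE rate there are 0.03 × 157 = 4.71 SADE patients. The expected number mistimed is 4.71 × 0.135 = 0.64 to 4.71 × 0.249 = 1.17.

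**Effect on the early curve.** Each mistimed patient lowers the curve by about 1/157 = 0.64 points between the wrong and the right date. As an illustration, take five SADEs on days 15, 30, 50, 70 and 95, with first AEs on days 15, 5, 10, 70 and 20, and 10% of patients censored evenly. The SADE-free estimate with right and wrong dates is 98.72% and 97.44% at day 30, 97.42% and 96.79% at day 90, and 96.77% and 96.79% at day 365. Three of the five are mistimed here, so this shows the shape of the error, not its expected size.

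**Effect at day 365.** Simulation with 4,000 runs per scenario, N = 157, 3% SADE, follow-up to day 365 ± 14. The figures are wrong minus right, mean shift in percentage points.

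| Drop-out (assumed) | Uniform onset | Early-weighted onset |
|---|---|---|
| 10% per year | +0.008 | +0.003 |
| 10% per 91 days | +0.030 | +0.011 |
| 40% terminated evenly over days 0–105 (stress case) | +0.113 | +0.039 |

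In the stress case the 95th percentiles are 0.43 and 0.20; single runs go higher and no bound is claimed. The shift is upward because more patients are still at risk on the earlier date.

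**If the flag is widened to 12 months but the date is kept.** Even if other AEs stop at day 91, a SADE after day 91 has an earlier AE with probability 1 − exp(−48/92) = 1 − exp(−0.522) = 0.407, or 0.300 with clustering.

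**Negative times.** AEs are collected from consent (CIP 8.3.6), and insertion may follow up to 4 weeks later (CIP 9.3). A first AE before insertion would give a negative event time.

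**The case against.** The strongest reply is that the deciding text is not visible. sar_aestdt_first carries footnote 3, which may already restrict it to endpoint events. SAP 1.2 allows labels to be shortened, and at least one label in the same table is plainly wrong: sar_hospndt_last carries an AE label. This stands as a limit. It rules out calling the derivation wrong, but it does not remove the conflict on the page.

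Other replies are partly right:

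- The Notes column of SAP 14.2 names AESTDT as a sort key for the AE evaluation file, so the onset date needed is at hand. That makes the fix easy, but no endpoint date or event time is defined there.
- The subtraction from insertion is stated in words and PRIMSTDT is defined in SAP 6.2. The mismatch between a date and a number of days is therefore secondary.
- The effect is small. The 95% interval half-width for 5 events in 157 is about 2.7 points, far above the mean shifts at day 365. This is accepted and is why the point is minor.
- Nothing in the documents supports 40% early termination; the predecessor study had 8.7% premature exits. It is a stress case only.
- The 3-month limit of AERELPET is a separate fault. That is correct, and the 0.407 figure applies only if that flag is widened. It is raised here because replacing the date alone would leave secondary endpoint 4 wrong.

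**Conclusion.** The point holds as a minor one. The wording of SAP 14.1 and the label of the variable it names cannot both be right. Used as labelled, the variable would time about 13% to 25% of SADE patients too early at the predecessor's AE rate (7% to 42% across the assumptions tried) and make the early curve fall too soon. The day-365 estimate moves little at 10% drop-out. The AE rate, clustering, onset patterns and drop-out are assumptions.

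The endpoint has no hypothesis, and the primary binomial test does not use this variable. The variable names for the 3-month curve in SAP 10.1 are blacked out, and no fault is claimed there.

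Whatever footnote 3 says, AERELPET cannot serve a 12-month endpoint. It is tied to the CIP 7.2.1 conditions, which exclude SADEs after the 3-month follow-up, so later SADEs would not count as events.

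**What to change.** 1. In SAP 14.1, replace sar_aestdt_first with a new derived variable: for each patient, the earliest AESTDT among AE evaluation records adjudicated as qualifying SADEs for the 12-month endpoint, minus PRIMSTDT, in days.
2. In SAP 14.2, add a flag, separate from AERELPET, for adjudicated SADEs through the 12-month follow-up.
3. In SAP 14.2, state that qualifying records are selected before sorting and removing duplicates, so that an earlier non-endpoint AE cannot displace the SADE.
4. If footnote 3 already limits sar_aestdt_first to endpoint events, correct its label in SAP 8. The 12-month flag is still needed.

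The cost is one derived variable, one adjudication flag and one sentence each in 14.1 and 14.2. No new patient data are needed: under CIP 8.1.3 the internal board already evaluates SADEs for this endpoint. The sample size does not change.
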